5.3 DRUG CONCENTRATION MEASUREMENTS AND PHARMACOKINETICS

Actual date and clock time of drug administration and exact time points of blood sampling will be documented in the CRFs by the medical personnel. The actual drug administration times and sampling times will be used for determination of pharmacokinetic parameters.

5.3.1 Assessment of pharmacokinetics

Pharmacokinetic profiles of BI 836880 (Part I and II) and BI 754091 (Part II) in plasma will be investigated after the first, second and fourth infusion cycle in Part I and the first and after the fourth infusion cycle in Part II. Standard plasma PK parameters as specified in Sections [2.1.3](#) and [2.2](#) will be calculated. Pharmacokinetic data may additionally be analyzed using population pharmacokinetic approaches. For this purpose data may also be combined with data from other trials. Modelling activities will be planned and documented separately according to internal and external guidelines and standard operating procedure (SOP). Exploratory pharmacokinetic analyses can be performed as necessary for safety review. In contrast to the final PK analysis, the exploratory analyses will be based on planned sampling times rather than on actual times; no supplementary subject information, e.g. on adverse events or concomitant medication, will be used in these analyses, and the outputs will not be validated. Minor discrepancies between interim and final results may therefore occur.

[figure not shown]
5.3.2 Methods of sample collection

The time points for collection of PK samples are given in Appendix [10.4](#). For quantification of analyte concentrations, approximately 3 mL of blood will be taken from a forearm vein into a blood drawing tube for each drug administered at the time points listed in the Appendix 10.4. Details of the sample collection, preparation, storage and shipment are described in the laboratory manual.

After completion of the trial the plasma samples may be used for further methodological investigations, e.g. for stability testing. However, only data related to the analyte and/or its metabolite(s) including anti-drug antibodies (if applicable) will be generated by these additional investigations. The study samples will be discarded after completion of the

Proprietary confidential information © 2019 Boehringer Ingelheim International GmbH or one or more of its affiliated companies

additional investigations but not later than 5 years upon the final study report has been signed.

5.7 APPROPRIATENESS OF MEASUREMENTS

All measurements performed during this trial are standard measurements and will be performed in order to monitor subjects' safety and to determine pharmacokinetic and pharmacodynamic parameters in an appropriate way. The scheduled measurements will allow monitoring of changes in vital signs, standard laboratory values, and ECG parameters that might occur as a result of administration of trial medication. The safety assessments are standard, are accepted for evaluation of safety and tolerability of an intravenously administered drug, and are widely used in clinical trials. The pharmacokinetic parameters and measurements outlined in Sections [2.1.3](#), [2.2](#), and [5.3](#) are generally used assessments of drug exposure. The biomarkers and pharmacodynamic parameters and measurements outlined in Section [5.4](#) are of exploratory nature only. The determination of the immunogenic response before or during treatment with NBEs is generally applied to monitor immunogenicity risks.

6. INVESTIGATIONAL PLAN

6.1 VISIT SCHEDULE

Patients must comply with all inclusion and exclusion criteria prior to the patient participation in the study (see Section [3.3](#)).

All patients should adhere to the visit schedule as specified in the [Flow Chart](#). In case a patient misses a visit within one treatment cycle and the patient belatedly reports to the investigator between the missed and the next scheduled visit, the delayed visit should be scheduled as soon as possible and documented with the actual date and the reason for the delayed visit. The next visit, should still take place at the time it was originally scheduled in this treatment cycle. In case the day of treatment administration (visit 1 of a cycle) is delayed, all subsequent visits of a cycle will be recalculated based on the actual date of treatment of the delayed cycle.

During the treatment phase, patients are required to be hospitalized under close surveillance with access to intensive care for at least 48 hours after the first administration of trial medication(s) to allow close monitoring for infusion-related reactions or other adverse events and availability of patients for PK visits. After good tolerability of the first cycle of trial medication, the investigator may evaluate the risk for an infusion-related reaction and other adverse events in view of relevant comorbidities or disease related symptoms, and may shorten the duration of surveillance to 8 hours for cycles 2, 3 and 4 (PK samples included) and at investigator's discretion for further cycles.

If pathological laboratory values or other issues require an additional unscheduled visit, a new eCRF page will be created for the unscheduled visit. At the unscheduled visit, it is sufficient to record only the clinical relevant labs/examinations performed.

6.2 DETAILS OF TRIAL PROCEDURES AT SELECTED VISITS

The investigations as outlined in the Flow Chart will be performed at the respective visits. Specific details to conduct of physical examination, collection of vital signs (including blood pressure measurement), laboratory investigations, assessment of ECG and echocardiography can be found in the subsections of Section [5.2](#).

Procedure for collection of blood samples for PK, [REDACTED] are given in Sections [5.3](#) and [5.4](#).

A more detailed overview of collection of blood samples for PK, [REDACTED] is given in Appendix [10.4](#).

6.2.1 Screening and run-in period(s)

Screening Period

The examinations required for the screening visit may be conducted within a time interval specified in the [Flow Chart](#). Prior to any other study related procedure, written informed consent must be obtained from the patient.

Baseline Conditions

Demographics (sex, birth date, race, and ethnicity where allowed), information on tobacco and alcohol use, and baseline conditions will be collected during the screening visit.

Medical History of cancer:

History of the patient's cancer will be obtained. The type of cancer, the date of the first histological diagnosis (month and year may be sufficient), and the primary tumour site will be reported on the eCRF. The differentiation grade (not specified, undifferentiated, poorly differentiated, moderately differentiated, well differentiated) obtained at the time of diagnosis and the location of metastatic sites as well as the stage according to the tumour, (lymph) node, and metastasis (TNM) classification will be provided as obtained at diagnosis and at trial screening. Previous surgeries will be reported.

Previously administered chemotherapy, tyrosine kinase inhibitor treatment, vaccine therapy, antibodies therapy, immune therapy, and hormone therapy will be reported, including start and end dates (month and year may be sufficient), as well as whether therapy was given as neoadjuvant, adjuvant, or palliative therapy. The date of tumour progression after previous lines of treatment will be recorded, if known.

Baseline information relevant to the disease history such as PD-L1 expression level, microsatellite instability (MSI), and tumour mutation burden (TMB) information will be collected in eCRF where available.

Other Medical History:

Past diseases and/or concomitant diagnoses relevant to patient's safety during the trial as judged by the Investigator will be recorded in eCRF.

Concomitant Medications:

Past medications relevant to patient's safety during the trial as judged by the Investigator will be recorded in eCRF. From the date of signature of the ICF, all concomitant medications will be recorded

6.2.2 Treatment period(s)

Please refer to the Flow Chart for a detailed presentation of each visit during the treatment period.

6.2.3 Follow-up period and trial completion

6.2.3.1 End of treatment (EoT) visit

The EoT visit will be performed as soon as possible but no later than 7 days after permanent discontinuation of the trial medication for any reason or e.g. when the Investigator decided with the patient to permanently discontinue the trial medication or became aware that the trial medication had been terminated.

The assessments of the EoT visit will then be performed instead of at the next planned visit.

If the patient finishes active treatment without having PD, tumour assessment/imaging must be performed at the time of EoT, unless it has been done within the past 4 weeks.

6.2.3.2 Safety follow-up visit

The safety follow-up visit is performed 42 (+3) days after the last administration of trial medication(s). The information collected at this visit must include all new AEs that occurred after the EoT visit, and a follow-up of AEs ongoing at EoT.

A patient will be considered as having completed the trial when any of the following applies:

- Completion of safety follow-up visit
- Lost to follow-up
- Withdrawal to be followed-up
- Death

7. STATISTICAL METHODS AND DETERMINATION OF SAMPLE SIZE

7.1 STATISTICAL DESIGN - MODEL

7.1.1 Statistical design – Part I (BI 836880 monotherapy dose finding part)

Part I of the trial will be designed as an open label study. The objective of the design is to determine the MTD defined as the highest dose with less than 25% risk of the true DLT rate being equal or above 0.33 (EWOC criterion). The part I dose-finding will be guided by a Bayesian 2-parameter logistic regression model with overdose control ([R13-4806](#); [R13-4803](#)).

The model is formulated as follows:

$$\text{logit}(\pi_d) = \log(\alpha) + \beta * \log(d/d^*),$$

where $\text{logit}(\pi) = \log(\pi/(1-\pi))$.

π_d represents the probability of having a DLT in the MTD evaluation period at dose d , $d^* = 720$ mg is the reference dose, allowing for the interpretation of α as the odds of a DLT at dose d^* , and $\theta = (\log(\alpha), \log(\beta))$ with $\alpha, \beta > 0$ is the parameter vector of the model.

The estimated probability of a DLT at each dose level from the model will be summarized using the following intervals:

Underdosing: [0.00, 0.16)

Targeted toxicity: [0.16, 0.33)

Over toxicity: [0.33, 1.00]

The BLRM-recommended dose for the next cohort is the level with the highest posterior probability of the DLT rate falling in the target interval [0.16, 0.33] among the doses fulfilling EWOC. Applying the EWOC criterion it should be unlikely (<25% posterior probability) that the DLT rate at that dose will exceed 0.33.

The MTD may be considered reached if one of the following criteria is fulfilled:

1. The posterior probability of the true DLT rate in the target interval [0.16 – 0.33] of the MTD is above 0.5, OR
2. At least 9 patients have been treated in this part, of which at least 6 at the MTD.

The SMC may recommend stopping the dose finding phase after the criterion for MTD is fulfilled. Further patients may be included to confirm this MTD estimate. If no DLT is observed at a dose of which the efficacy is considered sufficient, the SMC may decide to include additional number of patients at this dose level and to declare this dose as the dose recommended for further testing.

Since a Bayesian approach is applied, a prior distribution $f(\theta)$ for the unknown parameter vector θ needs to be specified.

The prior distribution for θ will be specified as a mixture of two bivariate normal distributions,

$$f(\theta) = a_1 f_1(\theta) + a_2 f_2(\theta)$$

with

$a_i, i = 1, 2$ the prior mixture weights ($a_1 + a_2 = 1$)

and

$$f_j(\theta) = \text{MVN}(\mu_j, \Sigma_j)$$

the multivariate normal distribution of the i -th component with mean vector μ_i and covariance matrix Σ_i , where

$$\Sigma_i = \begin{pmatrix} \sigma^2_{i,11} & \sigma_{i,11}\sigma_{i,22}\rho_i \\ \sigma_{i,11}\sigma_{i,22}\rho_i & \sigma^2_{i,22} \end{pmatrix}$$

Mixture prior distributions have the advantage that they allow for specification of different logistic dose-toxicity curves, therefore making the prior more robust.

Prior derivation:

To determine the prior distribution for θ , a meta-analytic predictive (MAP) approach will be used. Toxicity information on BI 836880 from the 1336-0001 is available. Exact details on the derivation of the prior distributions and on the evaluation of the model using hypothetical data scenarios and operating characteristics are provided in the statistical appendix, i.e., Section 10.5.1, a brief description is given here.

The historical data for 1336-0001 phase I as of 20 July 2018 can be found in [Table 7.1.1: 1](#).

Table 7.1.1: 1 Historical data from 1336-0001 as of 20 July 2018

Dose BI 836880 (mg)	N of patients treated	N of patients with DLTs during MTD evaluation period
40	2	0
120	2	0
360	2	0
720	17	0
1000	5	1

The following steps were performed to derive the prior distribution for θ :

- The MAP prior was derived using the information in Table 7.1.1: 1 allowing for moderate to substantial between-trial heterogeneity. This mixture component was assigned 90% mixture weight.
- A second, weakly informative component was added with 10% mixture weight. The weakly informative prior was derived to reflect a prior assumption that the median DLT rate at the starting dose of 360 mg would equal 10% and median DLT rate at 720 mg would equal 60%.

The prior distributions are given in [Table 7.1.1: 2](#). The corresponding prior probabilities of a DLT at different doses and the corresponding probability of underdosing, targeted dosing, and overdosing are shown in [Table 7.1.1: 3](#).

Table 7.1.1: 2 Prior distribution

Parameter	Means, standard deviations, correlation	Mixture weight
θ: component 1	(-2.263,0.116), (0.677,0.946), -0.076	0.9
θ: component 2	(0.405, 1.323), (2,1), 0	0.1

Table 7.1.1: 3 Prior probabilities of DLTs

Dose	Probability of true DLT rate in			Quantiles				
	[0,0.16)	[0.16,0.33)	[0.33,1]	Mean	StD	2.5%	50%	97.5%
360 mg	0.925	0.049	0.026	0.069	0.109	0.000	0.041	0.336
720 mg	0.751	0.169	0.080	0.154	0.176	0.027	0.100	0.844

The prior may be updated once the trial has started in case new data that can be used will be available. The prior that is used for each BLRM analysis for the SMC meetings will be documented in the SMC minutes, the prior used for the final analysis will be documented in the Trial Statistical Analysis Plan (TSAP).

7.1.2 Statistical design – Part II (BI 836880 and BI 754091 combination dose finding)

Part II of the trial will be performed as an open label single arm study. The primary objective of the design is also to determine the MTD in Japanese patients of BI 836880 in combination with BI 754091. To determine the MTD, patients are entered sequentially into escalating dose cohorts. The dose-finding will be guided by a Bayesian 5-parameter logistic regression model with overdose control. The model is defined as follows. Let $\pi_{1,d1}$ be the probability of having a DLT when giving dose d_1 of BI 836880 as monotherapy, and $\pi_{2,d2}$ the probability of having a DLT when giving dose d_2 of the combination partner BI 754091 as monotherapy, respectively. A logistic regression model is used to model the dose-toxicity relationship for each component individually:

BI 836880 part:

$$\text{logit}(\pi_{1,d1}) = \log(\alpha_1) + \beta_1 \log(d_1/d_1^*)$$

BI 754091 part:

$$\text{logit}(\pi_{2,d2}) = \log(\alpha_2) + \beta_2 \log(d_2/d_2^*)$$

where $\text{logit}(\pi) = \log(\pi / (1 - \pi))$, the reference doses $d_1^* = 500 \text{ mg}$ and $d_2^* = 240 \text{ mg}$ are set for BI 836880 and BI 754091, respectively.

Assuming no toxicity interaction between the two compounds, the probability of a DLT when giving the combination of dose d_1, d_2 is obtained as

$$\pi_{12,d1,d2}^0 = \pi_{1,d1} + \pi_{2,d2} - \pi_{1,d1}\pi_{2,d2}$$

with corresponding odds

$$\text{odds}(\pi_{12,d1,d2}^0) = \pi_{12,d1,d2}^0 / (1 - \pi_{12,d1,d2}^0)$$

In order to account for a potential positive (higher toxicity than expected under independence) or negative (lower toxicity than expected under independence) interaction between BI 836880 and BI 754091, a dose-dependent interaction term $-\infty < \eta < \infty$ is introduced to the model by the following definition:

$$\text{odds}(\pi_{12,d1,d2}) = \text{odds}(\pi_{12,d1,d2}^0) \exp(\eta d_1/d_1^* d_2/d_2^*)$$

and $\pi_{12,d1,d2}$ is used in the likelihood

$$r_{d1,d2} \sim \text{Binomial}(n_{d1,d2}, \pi_{12,d1,d2})$$

where $r_{d1,d2}$ denotes the variable describing the observed number of DLTs from $n_{d1,d2}$ patients at the dose combination d_1, d_2 .

Since a Bayesian approach is applied, prior distributions f for each of the parameter vectors $\theta_1 = (\log(\alpha_1), \log(\beta_1))$, $\theta_2 = (\log(\alpha_2), \log(\beta_2))$ and for the interaction term η need to be specified.

The prior distributions for θ_1 and θ_2 will be specified as mixtures of two multivariate normal distributions, i.e.

$$f(\theta_k) = a_{1,k} f_1(\theta_k) + a_{2,k} f_2(\theta_k)$$

with

$a_{1,k}, a_{2,k}$ the prior mixture weights, $k=1,2$ and

$$f_i(\theta_k) = \text{MVN}(\mu_{ik}, \Sigma_{ik}) \quad (k=1,2),$$

the multivariate normal distribution of the i -th component with mean vector μ_{ik} and covariance matrix Σ_{ik} , where

$$\Sigma_{ik} = \begin{pmatrix} \sigma_{ik,11}^2 & \sigma_{ik,11}\sigma_{ik,22}\rho_{ik} \\ \sigma_{ik,11}\sigma_{ik,22}\rho_{ik} & \sigma_{ik,22}^2 \end{pmatrix}$$

Mixture prior distributions have the advantage that they allow for specification of different logistic dose-toxicity curves, therefore making the prior more robust.

A meta-analytic approach will be used for the prior specification of η .

The estimated probability $\pi_{12,d1,d2}$ of a DLT at each dose combination d_1, d_2 from the model will be summarised using the following intervals:

Under dosing: [0.00, 0.16)

Targeted toxicity: [0.16, 0.33)

Over dosing: [0.33, 1.00]

The BLRM-recommended dose for the next cohort is the level with the highest posterior probability of the DLT rate falling in the target interval [0.16, 0.33) among the doses fulfilling EWOC. Applying the EWOC criterion it should be unlikely (<25% posterior probability) that the DLT rate at that dose will exceed 0.33.

As described The MTD may be considered to be reached if one of the following criteria is fulfilled:

1. The posterior probability of the true DLT rate in the target interval [0.16 – 0.33) of the MTD is above 0.5, OR
2. At least 9 patients have been treated in the study, of which at least 6 at the MTD.

Prior derivation:

To determine the prior distributions for θ_1 , θ_2 and η a meta-analytic predictive (MAP) approach will be used. Toxicity information on BI 836880 monotherapy from the study 1336-0001, and the Part 1 of this study, toxicity information on BI 754091 monotherapy from the studies 1381-0001 and 1381-0004, and toxicity information on the combination of BI 836880 and BI 754091 from study 1336-0011 will be incorporated. Exact details on the evaluation of the model using hypothetical data scenarios and operating characteristics are provided in the statistical appendix; a brief description is given here.

The historical data for BI 836880 can be found in [Table 7.1.1: 1](#). For BI 754091, the historical data can be found in Tables [7.1.2: 2](#) and [7.1.2: 3](#). Expected historical data for the combination of BI 836880 and BI 754091 can be found in [Table 7.1.2: 4](#). Since data from 1336-0012 Part 1 and 1336-0011 were not yet available by the time of finalization of the CTP, data as is might be observed in future in these trials will be used as dummy data. This dummy data will be replaced by actual data as soon as it becomes available. Whenever BLRM calculations are performed for Part 2 of 1336-0012, all available information will be used and the resulting prior distribution will be documented.

Table 7.1.2: 1 Hypothetical data expected from 1336-0012 part 1

Dose BI 836880 (mg)	N of patients treated	N of patients with DLTs during MTD evaluation period
360	6	1
720	3	2

Table 7.1.2: 2 Preliminary data from 1381-0001

Dose BI 754091 (mg)	N of patients treated	N of patients with DLTs during MTD evaluation period
80	3	0
240	34	0
400	3	0

Table 7.1.2: 3 Preliminary data from 1381-0004

Dose BI 754091 (mg)	N of patients treated	N of patients with DLTs during MTD evaluation period
240	6	0

Table 7.1.2: 4 Hypothetical data expected from 1336-0011

Dose BI 836880 (mg) / BI 754091 (mg)	N of patients treated	N of patients with DLTs during MTD evaluation period
360 / 240	1	1
500 / 240	0	0
720 / 240	0	0

The following steps were performed to derive the prior distribution for Part 2:

- 1) The meta-analytic predictive prior was derived for both compounds and for the interaction parameter η using the information in Tables 7.1.2: 1 – 7.1.2: 4, allowing for moderate to substantial between-trial heterogeneity, tau parameters are assumed to be normally distributed with mean $\log(0.25)$ and SD $\log(2)/1.96$. See a reference ([R18-3210](#)) for details on the MAP prior. These prior components were assigned 90% mixture weight for both compounds.
- 2) A second, weakly informative prior component was added with the same mean values as the MAP prior, standard deviation (2, 1) and correlation 0. This mixture component was assigned 10% mixture weight

The resulting parameters of the prior distributions for four combination levels, i.e., (120/240, 360/240, 500/240, 720/240), are given in [Table 7.1.2: 5](#). The corresponding prior probabilities of a DLT at different dose combinations and the corresponding probabilities of under toxicity, targeted toxicity and over toxicity are shown in [Table 7.1.2: 6](#). As can be seen from Table 7.1.2: 6, the dose combination 120 mg BI 836880 and 240 mg BI 754091 has prior probability of over toxicity below 25%. It fulfils the overdose criterion and is therefore a suitable starting dose combination.

Table 7.1.2: 5 Prior Distribution

Parameter	Prior distributions Means, standard deviations, correlation	Mixture weight
log(α_1), log(β_1): component 1	(-1.877,-0.574), (0.983, 0.893), -0.145	0.9
log(α_1), log(β_1): component 2	(-1.877,-0.574), (2,1), 0	0.1
log(α_2), log(β_2): component 1	(-1.500, 1,213), (1.070, 1.034), 0.387	0.9
log(α_2), log(β_2): component 2	(-1.500, 1,213), (2,1), 0	0.1
η	0.466, 0.989	N/A

Table 7.1.2: 6 Prior probabilities of DLTs

Dose (mg)	Dose (mg)	Probability of true DLT rate in			Descriptive statistics				
		[0,0.16)	[0.16,0.33)	[0.33,1]	Mean	SD	2.5%	50%	97.5%
BI 836880	BI 754091								
120	240	0.486	0.327	0.187	0.209	0.162	0.023	0.165	0.637
360	240	0.280	0.311	0.409	0.318	0.213	0.035	0.273	0.814
500	240	0.134	0.213	0.653	0.468	0.255	0.059	0.454	0.933
720	240	0.077	0.100	0.822	0.680	0.299	0.065	0.774	1.000

The prior will be updated once the trial has started in case new data that can be used will be available. The prior that is used for each BLRM analysis for the SMC meetings will be documented in the SMC minutes, the prior used for the final analysis will be documented in the TSAP.

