3.3.4.1 Discontinuation of trial treatment

An individual patient will discontinue trial treatment if:

- The patient wants to discontinue trial treatment, without the need to justify the decision.
- The patient has repeatedly shown to be non-compliant with important trial procedures and, in the opinion of both, the investigator and sponsor representative, is not willing or able to adhere to the trial requirements in the future.
- The patient needs to use concomitant medication that interferes with the investigational medicinal product or trial assessments. Refer to Section [4.2.2.1](#) for prohibited concomitant medications.
- The patient can no longer receive trial treatment for medical reasons (such as surgery, adverse events, other diseases, or pregnancy). Refer to Section [4.1.6](#) for AEs that require treatment discontinuation.
- The patient experiences unequivocal PD by RECIST v1.1 and/or iRECIST (iRECIST applies to Part II only). Refer to Section [5.1.1](#) for details.

Even if the trial treatment is discontinued, the patient remains in the trial and, will undergo the procedures for the end of treatment (EoT) visit and follow up as outlined in the [Flow Chart](#) and Section [6.2.3](#).

For all patients the reason for withdrawal from trial treatment (e.g. AEs) must be recorded in the CRF. These data will be included in the trial database and reported.

During the dose finding part, patients withdrawn for a reason other than having a DLT or patients who miss more than one visit during MTD evaluation period may be replaced after discussion in the SMC if the information that needed to be collected during that visit is not available and makes the patient non-evaluable for the PK analyses or safety parameters (including evaluation for DLTs).

Patients who come off trial due to a DLT will not be replaced.

If a patient should become pregnant during the trial, the study treatment must be immediately stopped. The patient will be followed up until delivery or termination of pregnancy (see Section [5.2.9.2.3](#) for information on pregnancy forms). The data of the patient will be collected and reported in the electronic case report form (eCRF) until the last patient's last visit and any events occurring thereafter will be reported in the BI drug safety database.

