4.1.8 Definition of evaluable patient

For decisions on dose escalation, an evaluable patient is defined as a patient who has received BI 836880 or BI 836880 plus BI 754091 and either:

- has completed cycle 1 without experiencing DLT

OR

- has experienced DLT during cycle 1

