7.3 PLANNED ANALYSES

No per protocol set will be used in the analysis. However, important protocol deviations will be summarised. The TSAP will specify the important protocol deviations in detail.

For the determination of the MTD, only MTD evaluable patients will be considered. For the analysis of secondary and further endpoints, all patients in the treated set (i.e. patients treated with at least one dose of trial medication) will be included in the analysis. Any other analysis sets will be defined in the TSAP.

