7.3.1 General considerations

Treated set includes all patients who were treated with at least one dose of trial medication. The pharmacokinetic parameters listed in Sections [2.1.3](#) and [2.2.2](#) will be calculated according to the BI SOP ‘Standards and processes for analyses performed within Clinical Pharmacokinetics/Pharmacodynamics’ ([001-MCS-36-472](#)). PK analyses will be performed using validated software programs, normally, Phoenix WinNonlin [REDACTED] with applications validated for the respective purpose. Graphs and tables will be generated using validated customised [REDACTED] macros or appropriate graphic software.

[figure not shown]

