7.3.2 Primary endpoint analyses

In order to identify the MTD, the number of patients with DLTs during the MTD evaluation period of Part I and Part II at each dose level must be presented. Patients who discontinue during the first treatment course for reasons other than DLTs will be excluded from the determination of MTD.

In addition, the number of patients with DLTs that occurred during the entire treatment period will be also summarised.

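### MTD criterion 2 counts treated patients, but only evaluable patients inform the MTD, so it can be met with fewer than 6 informative patients at the dose

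*Protocol*

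**What the plan says.** Protocol 7.1.1 introduces two alternative criteria with the words "The MTD may be considered reached if one of the following criteria is fulfilled". Criterion 1 asks for a posterior probability above 0.5 that the DLT rate lies in the target interval. Criterion 2 is a head count: "At least 9 patients have been treated in this part, of which at least 6 at the MTD". Protocol 7.1.2 gives the Part II version as "At least 9 patients have been treated in the study, of which at least 6 at the MTD". SAP 5.1 repeats the count of treated patients for both parts.

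Protocol 7.3.1 fixes the broad term: "Treated set includes all patients who were treated with at least one dose of trial medication". Protocol 4.1.8 fixes the narrow one: "an evaluable patient is defined as a patient who has received BI 836880 or BI 836880 plus BI 754091 and either" completed cycle 1 without a DLT or had a DLT in cycle 1.

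The MTD analysis uses the narrow group. Protocol 7.3 states "For the determination of the MTD, only MTD evaluable patients will be considered", and 7.3.2 adds "Patients who discontinue during the first treatment course for reasons other than DLTs will be excluded from the determination of MTD". SAP 6.3 and 7.4 agree. Under Protocol 3.3.4.1, patients who leave early without a DLT or miss more than one visit in the evaluation period "may be replaced after discussion in the SMC". Table 1.4.2: 1 likewise leaves evaluability and replacement to SMC discussion.

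**The concern.** The count that lets the MTD be called reached and the model that estimates it use different populations. A patient who leaves in cycle 1 without a DLT adds one to criterion 2 and nothing to the Bayesian logistic regression model (BLRM). The plan expects such patients: Protocol 3.1 allows escalation when only 2 patients in a cohort are evaluable.

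This matters because criterion 2 will often be the one in use. The largest target-interval probability printed in the plan's own data scenarios is 0.416 in Part I (Table 10.5.1: 1) and 0.440 in Part II (Table 10.5.2: 1), so none of them meets criterion 1. If criterion 2 is meant to secure a minimum of DLT information at the declared dose, a count of treated patients does not secure it.

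**Working it through.** The thresholds 9 and 6 are counting rules. The documents derive them from no formula, so there is no figure to reproduce for the rule itself.

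**1. How often would the counts differ?** The non-evaluable rate q is an assumption, taken as 5% to 20%, independent between patients, with no replacement. Among 6 treated at the dose:

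- P(fewer than 6 evaluable) = 1 − (1 − q)^6
- P(4 or fewer evaluable) = 1 − (1 − q)^6 − 6q(1 − q)^5

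| q | fewer than 6 | 4 or fewer |
|---|---|---|
| 5% | 26.5% | 3.3% |
| 10% | 46.9% | 11.4% |
| 15% | 62.3% | 22.4% |
| 20% | 73.8% | 34.5% |

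**2. What information is lost?** At a true DLT rate of 0.33, the lower edge of the overdose interval, P(at most 1 DLT in n) = 0.67^n + n(0.33)(0.67)^(n−1). This is 0.358 for n = 6, 0.468 for n = 5, 0.599 for n = 4 and 0.745 for n = 3.

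**3. Does the overdose limit still work? Part I.** Inputs are the model in Protocol 7.1.1 and the prior in Table 7.1.1: 2. Check against Table 7.1.1: 3: the prior P(DLT rate ≥ 0.33) comes out at 0.027 for 360 mg (printed 0.026) and 0.081 for 720 mg (printed 0.080). With 0/3 DLTs at 360 mg, the posterior P(DLT rate ≥ 0.33) at 720 mg is:

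| Evaluable at 720 mg | 1 DLT | 2 DLTs |
|---|---|---|
| 6 | 0.013 | 0.071 |
| 5 | 0.020 | 0.112 |
| 4 | 0.033 | 0.187 |

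Two DLTs in 3 evaluable give 0.334, above the 0.25 limit. One caveat: several posteriors in Table 10.5.1: 1 do not reproduce from the printed prior (scenario 3, 360 mg: 0.386 against 0.241; scenario 6, 720 mg: 0.334 against 0.319). These Part I figures therefore rest on the prior as printed.

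**4. Part II.** Table 7.1.2: 6 is reproduced closely only if the two compounds' rows in Table 7.1.2: 5 are exchanged: overdose probabilities 0.185, 0.404 and 0.651 at 120/240, 360/240 and 500/240, against printed 0.187, 0.409 and 0.653. On that basis, with 0/3 DLTs at 120/240 and one DLT at 360/240, P(overdose) at 360/240 is 0.121 with 6 evaluable, 0.164 with 5 and 0.220 with 4. With 3 it is 0.293 (printed 0.295 in Table 10.5.2: 1, scenario 5), which fails the limit. With the rows as printed, the values for 6, 5 and 4 are 0.173, 0.227 and 0.296, and the last fails.

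Steps 1 and 2 do not depend on either prior.

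**The case against.** The strongest reply is that the wording is merely loose. Criterion 2 is part of determining the MTD, and Protocol 7.3 restricts that to evaluable patients. SAP 6.3 calls its MTD set a treated set yet requires evaluability. The protocol also uses the word loosely elsewhere: the column headed as treated in Table 7.1.1: 1 sums to 2 + 2 + 2 + 17 + 5 = 28, the same patients that Table 4.1.2.1: 1 calls evaluable, while the text of 4.1.2.1 says 29 were treated. This shows what the sponsor may well mean. It does not settle it, because no passage ties the count in criterion 2 to evaluable patients, and Protocol 7.3 itself contrasts the two terms. That 6 informative patients are intended remains an inference.

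The second reply is that the safeguards lie elsewhere, and this stands. The criterion is permissive, Protocol 4.1.4 requires SMC consensus, further patients may be added to confirm the estimate, and criterion 1 has no minimum number at all. So 6 evaluable patients is not an absolute floor under either wording.

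A reader might go further and infer that the wording nearly doubles the overdose risk, from 0.121 to 0.220. The documents do not support that. The rise needs two lost patients, which at an assumed 10% rate has probability about 11%, not 47%. It holds one DLT fixed while the denominator shrinks, so the observed rate itself rises from 1/6 to 1/4; with no DLT at 360/240 the figure moves only from 0.027 to 0.057. In Part I the one-DLT figures stay far below 0.25. Where the data become thin enough to be worrying, as with 1/3 in Part II, the overdose limit blocks the dose.

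**Conclusion.** The point holds as a mismatch in a decision rule for the primary endpoint. As written, criterion 2 can be satisfied with 5, 4 or fewer informative patients at the declared dose. Over the assumed 5% to 20% non-evaluable range without replacement, the chance of falling short of 6 is 26% to 74%; any replacement by the SMC lowers it. The consequence is a less precise MTD declaration, shown by the rise from 0.36 to 0.60 in the chance of at most one DLT at a true rate of 0.33 when evaluable patients fall from 6 to 4.

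It is not a failure of overdose control. The overdose limit is computed on evaluable data whatever criterion 2 counts, and the SMC decides. Severity is low to moderate. The conclusion about the count rests on the text alone; its size rests on the assumed rate and, for the posterior figures, on the priors as described above.

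**What to change.** In criterion 2 of Protocol 7.1.1, Protocol 7.1.2 and SAP 5.1 (both parts), replace *treated* by *evaluable for MTD (Section 4.1.8)*: at least 9 evaluable patients in the part, of whom at least 6 at the MTD. The same edit should align the Part II scope, since Protocol 7.1.2 counts over the study and SAP 5.1 over the part.

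The cost is an occasional replacement patient, which Protocol 3.3.4.1 already allows. Dividing by 1 − q and rounding up, 6 evaluable need about 7 treated at a 5% or 10% rate (6/0.90 = 6.7) and 8 at 15% or 20% (6/0.80 = 7.5). Nine evaluable need about 10 at 5% or 10%, 11 at 15% and 12 at 20%. Protocol 7.6 already foresees that more patients than the approximate numbers may be needed. If the sponsor already counts evaluable patients, the edit only records existing practice.
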